### 1.2 Administrative Information

Protocol Number: HW006  
 Revision Number: 7.3  
 Protocol Date: 24 Oct 2018  
 Investigational Product: HeartWare® Ventricular Assist Device System (HVAD)

### 1.3 Amendment History

Date	Amendment Number	Amendment Type
18 November 2013	1.0	Original Protocol
04 February 2014	2.0	Revised Submission
07 April 2014	3.0	Revised Submission
07 May 2014	4.0	Revised Submission
11 Aug 2014	5.0	Revised Submission
15 Sep 2014	6.0	Revised Submission
3 Feb 2015	7.0	Revised Submission
06 July 2015	7.1	Revised Submission
10 Feb 2016	7.2	Revised Submission
24 Oct 2018	7.3	Revised Submission

CONFIDENTIAL

## 2. STUDY SUMMARY

Name of Sponsor(s): Medtronic / HeartWare (hereafter referred to as HeartWare)	
Title of protocol: A Prospective, Single Arm, Multi-Center Clinical Study in Collaboration with the InterAgency Registry for Mechanically Assisted Circulatory Support (INTERMACS®) to Evaluate the Thoracotomy Implant Technique of the HeartWare HVAD® System in Patients with Advanced Heart Failure	
Study Number: HW006	
Number of Subjects: 145 subjects implanted via thoracotomy with the HeartWare HVAD® System. It is anticipated that each site will enroll at least 1 subject. No site will implant more than 20 patients into the study without prior written approval from HeartWare.	Number of Sites: Up to 30 Sites in the US and 1 site in Canada
Study Design: This is a multi-center, prospective, single arm study that will evaluate the thoracotomy implant technique in up to 145 subjects implanted via thoracotomy with the HeartWare HVAD® System and enrolled in the InterAgency Registry for Mechanically Assisted Circulatory Support (INTERMACS®) protocol and database.  All participating centers will be current enrolled INTERMACS® sites in good standing and will follow the INTERMACS® protocol and procedures.	
Primary Endpoint: The primary endpoint is success at 6 months defined as all enrolled and implanted subjects: 
 
• Alive on the originally implanted device at 6 months, and the subject has not had a stroke with a modified Rankin Scale <math>\geq 4</math> (assessed <math>\geq 3</math> months post stroke event); or
 
• Transplanted by Month 6, and the subject has not had a stroke with a modified Rankin Scale <math>\geq 4</math> (assessed <math>\geq 3</math> months post stroke event); or
 
• Explanted for recovery by Month 6, and the subject has not had a stroke with a modified Rankin Scale <math>\geq 4</math> (assessed <math>\geq 3</math> months post stroke event).
 
 All subjects with stroke events from implant to Month 6 will be required to remain in follow-up until the post-stroke mRS measure ( $\geq 3$ months post stroke event) is obtained, even if this occurs after the 6-month visit. If a stroke subject is alive at 6 months, but dies before the post-stroke mRS is obtained, the subject will be considered a failure with regard to the primary endpoint.	
Secondary Endpoint: The secondary endpoint is an improvement in the mean length of initial hospital stay (initial recovery and step down unit) for all enrolled and implanted subjects. The mean length of initial hospital stay is estimated to be 26.1 days for median sternotomy subjects.	

[REDACTED]
	

[REDACTED]
	

[REDACTED]
	

[REDACTED]
	

[REDACTED]
	

[REDACTED]
	

[REDACTED]
	

[REDACTED]
	

[REDACTED]
	

[REDACTED]
	

[REDACTED]
	

[REDACTED]
	

[REDACTED]
	

[REDACTED]
	

Safety Assessments:
 
Safety assessments will be collected according to the INTERMACS® protocol and procedure, as summarized in Section 9.
	

Device: HeartWare® System
 
The HeartWare® System is an implantable ventricular assist device, with the following major components: Implantable Centrifugal Rotary Blood Pump (HVAD® Pump) with Inflow and Outflow Conduits, Controller and Power Sources, Monitor, Power Sources, Battery Charger, Surgical Tools and Carrying Case.
	

Intended Use:
 
The HeartWare® HVAD is intended for use as a bridge to cardiac transplantation in patients who are at risk of death from refractory end-stage left ventricular heart failure.
 
The HeartWare® HVAD is designed for in-hospital and out-of-hospital settings, including transportation via fixed wing aircraft or helicopter.
 
The HeartWare® HVAD is contraindicated in patients who cannot tolerate anticoagulation therapy.
	

Period of Evaluation:
 
Subjects will be followed according to the INTERMACS® protocol and standard of care at the enrolling institution. Data recorded in the INTERMACS® database to the primary endpoint at 6 months post implant of the HeartWare® HVAD will be evaluated.
 
 
• Subjects who have been transplanted prior to month 6 will be considered complete at the primary endpoint time-point.
 
• Subjects, who have a device exchange prior to month 6, will be evaluated according to the original implant date.
 
• Subjects who remain on device support after the primary endpoint time-point, either the original device or exchange device, will be followed according to the INTERMACS® protocol until transplant, or until 2.5 years post implant of the original device. A subject's study participation is considered complete at either the time of induction of anesthesia for transplant, or at the 2.5 year post implant visit.
 
• Subjects who have been explanted for recovery prior to month 6 will be followed until their next scheduled follow-up visit according to the INTERMACS® protocol, at which time their participation in the study is considered complete.
 
• The per-protocol analysis population will include those thoracotomy subjects with the outflow in the ascending aorta only. As a result, enrollment may exceed sample size requirements.
 
• The per-protocol analysis population will include those thoracotomy subjects with the procedure performed on-pump only. As a result, enrollment may exceed sample size requirements.
 
 
Subject data will be evaluated for a maximum of 2.5 years.
	

Estimated start date: October 2014
	
Estimated end date: October 2018

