\*Events that have an onset date of 0-30 days and which reoccur in the same patient past 30 days are counted in both 0-30 day and 31-180 day periods.

CONFIDENTIAL

There were eight subject deaths during the 180-day study period. Six deaths occurred in subjects with their originally implanted device and two deaths occurred after device exchange. There were 26 device malfunctions reported for 20 patients during the study period. Seven (5.0%) were due to the LVAD component; of these 6 involved thrombosis events, necessitating exchange.

The pre-specified primary endpoint analysis was a comparison of success rates using a non-inferiority margin of 15%. In the HVAD group the success rate in the Intent-To-Treat (ITT) / Safety Population at 180 days was 90.7% (127/140) and in the Per Protocol population 92.0% (126/137). The success for both Safety and Per Protocol populations in the Control group was 90.1% (448/497). The Primary analysis found that the 95% one-sided upper confidence limit (UCL) on the difference in success rates between HVAD group and controls was 4.5% for the Safety population and 0.9% for the Per Protocol population. Each of these limits was less than the 15% non-inferiority margin ( $p < 0.0001$ ).

Survival was defined as transplanted, or alive on device support, or alive after device explant for recovery. The overall Kaplan-Meier survival at 180 days in the HVAD group was 93.9% in the Safety population and 94.2% in the Per Protocol population. The corresponding survival for the INTERMACS control group was 90.2%. In addition survival status at Day 180 was assessed for all HeartWare® HVAD patients irrespective of meeting a predefined outcome (transplant or explant). There were 130/140 (92.9%) of patients alive at day 180 (88/140 were alive on the original device, 5/140 were alive post device exchange, and 37/140 were alive post-transplant).

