### 6.3 Primary Endpoint

The primary endpoint is success at 6 months defined as all enrolled and implanted subjects:

- Alive on the originally implanted device at 6 months, and the subject has not had a stroke with a modified Rankin Scale  $\geq 4$  (assessed  $\geq 3$  months post stroke event); or
- Transplanted by Month 6, and the subject has not had a stroke with a modified Rankin Scale  $\geq 4$  (assessed  $\geq 3$  months post stroke event), or
- Explanted for recovery by Month 6, and the subject has not had a stroke with a modified Rankin Scale  $\geq 4$  (assessed  $\geq 3$  months post stroke event).

All subjects with stroke events from implant to Month 6 will be required to remain in follow-up until the post-stroke mRS measure ( $\geq 3$  months post stroke event) is obtained, even if this occurs after the 6-month visit. If a stroke subject is alive at 6 months, but dies before the post-stroke mRS is obtained, the subject will be considered a failure with regard to the primary endpoint.

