## 11.2 Sample Size Justification

### **Primary Endpoint:**

Success at 6 months is estimated to be 86% compared to a performance goal of 77.5%. Using an exact binomial test, with a one-sided alpha of 0.05, and 80% Power, a sample size of 145 implanted subjects is required.

The target success estimate of 86% is based on the following:

- The primary endpoint observed in the final BTT IDE Report for the more recent BTT CAP population (N=242), resulted in a success prevalence of 85.8% (205 out of 239 eligible subjects) for sternotomy subjects.
- Post-approval data from the INTERMACS Registry (through Q2 2014), indicates similar results for the sternotomy population of 88.0% (396/450) with a lower prevalence of success for the small subset of thoracotomy (83.3%, 55/66) and thoracotomy on-pump (82.6%, 38/46) subjects.
- The INTERMACS Federal Partners Report (from Q1 2014) indicates an 85% Kaplan-Meier survival estimate at 6 months. This is not the same as “success” in that post-exchange survival is considered.
- The INTERMACS Industry Report for HeartWare (from Q2 2014) indicates an 88% Kaplan-Meier survival estimate at 6 months. This is not the same as “success” in that post-exchange survival is considered.

Success will be met if the lower bound of the one-sided exact 95% confidence limit is greater than 77.5%.

For exploratory purposes, the primary endpoint will also be assessed and observed by:

- Site
- CPB (on pump, off pump)
- Outflow location

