## Device Malfunction:

A **Device Malfunction** occurs when any component of the MCSD system ceases to operate to its designed performance specifications or otherwise fails to perform as intended. Performance specifications include all claims made in the Instructions for Use.

Device malfunctions can be further defined as **major** or **minor**:

1. **Major device malfunction**, otherwise known as failure, occurs when one or more of the components of the MCSD system either directly causes or could potentially induce a state of inadequate circulatory support (low cardiac output state) or death. A failure that was iatrogenic or recipient-induced will be classified as an Iatrogenic/Recipient-Induced Failure. A device malfunction or failure is considered major when one of the following conditions occurs:
  - a. Suspected or confirmed pump thrombus (see below)
  - b. Urgent transplantation (immediate 1A listing for transplant)
  - c. Pump replacement
  - d. Pump explant
  - e. Breach of integrity of drive line that required repair
  - f. Death
2. **Minor device malfunction** includes inadequately functioning external components which require repair or replacement but do not result in 1a-f. Device malfunction does not apply to “routine” maintenance which includes repair/replacement of: external controller, pneumatic drive unit, electric power supplies, batteries and interconnecting cables.

**Pump Thrombus** represents a special case of major device malfunction and can be delineated as **suspected pump thrombus** or **confirmed pump thrombus**. Pump thrombus will be classified as “SUSPECTED” (see definition below) based upon clinical, biochemical, or hemodynamic findings or “CONFIRMED” (see definition below) based upon device inspection or incontrovertible radiologic studies or absence of appropriate Doppler flow signals that confirms thrombus within the device or its conduits that results in or could potentially induce circulatory failure.

1. **Suspected pump thrombus** is a pump-related malfunction in which clinical or MCSD parameters suggest thrombus on the blood contacting components of the pump, cannulae, or grafts. Signs and symptoms should include at least 2 of the 3 following criteria:
  - a. **Presence of hemolysis**
  - b. **Presence of heart failure not explained by structural heart disease**
  - c. **Abnormal pump parameters**

Suspected pump thrombus should be accompanied by 1 or more of the following events or interventions:

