2.4.1. Primary Endpoint

The primary endpoint is success at 6 months for all enrolled and implanted subjects. Success is defined as follows:

- Alive on the originally implanted device at 6 months, and the subject has not had a severe stroke; or
- Transplanted by Month 6, and the subject has not had a severe stroke prior to transplant; or
- Explanted for recovery by Month 6, and the subject has not had a severe stroke prior to explant for recovery.

All subjects with stroke events from implant to Month 6 will be required to remain in study follow-up until the post-stroke mRS measure (≥ 3 months post stroke event) is obtained, even if this occurs at the next expected follow-up visit. If a stroke subject is alive at 6 months, but dies before the post-stroke mRS is obtained, the subject will be considered a failure with regard to the primary endpoint.

A stroke is considered severe if either:

- The first mRS score assessed ≥ 3 months post stroke event is ≥ 4 ; or

- The follow-up (≥ 3 months post stroke event) mRS score is missing and the day-of-event mRS is ≥ 4 .

Specifically, any subject experiencing any of the following events will be considered a failure:

- Death by any cause prior to 183 days post-implant and prior to transplant or explant for recovery
- A severe stroke occurring prior to 183 days post-implant and prior to transplant or explant for recovery
- A stroke followed by death within 91 days post-event occurring prior to 183 days post-implant and prior to transplant or explant for recovery

Subjects with a stroke with no available mRS and no death ≥ 91 days post-stroke occurring prior to 183 days post-implant and prior to transplant or explant for recovery will be considered missing in the primary analysis.

All subjects with at least 182 days of documented follow-up without meeting any of the above failure criteria will be considered a success. Subjects not considered a success or a failure will be excluded from the analysis.

N.B. As INTERMACS only includes visits every 6 months starting at the 6 month visit, it should be noted that should a stroke occur after 3 months, a post-event mRS score may not be obtained until the 12 month visit.

Hypotheses:

$$H_0: \pi_T \leq 77.5\%$$

$$H_a: \pi_T > 77.5\%$$

where π_T = the proportion of the patient population experiencing success for the Thoracotomy group.

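### The primary endpoint treats device exchange before Month 6 inconsistently: two of its three success routes ignore exchange, and the SAP scoring rule ignores it altogether

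*Protocol*

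**What the plan says.** The definition appears in Protocol sections 2, 6.3 and 11.1.2 and in SAP 1.2 and 2.4.1. Three bullets are joined by *or*:

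- The first is "Alive on the originally implanted device at 6 months", without a disabling stroke.
- The second, in the Protocol, is "Transplanted by Month 6, and the subject has not had a stroke with a modified Rankin Scale" at or above 4. In SAP 2.4.1 it is "Transplanted by Month 6, and the subject has not had a severe stroke prior to transplant".
- The third, in the Protocol, is "Explanted for recovery by Month 6, and the subject has not had a stroke with a modified Rankin Scale" at or above 4.

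Only the first names the original device.

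On exchange itself, Protocol sections 2 and 7.2 say "Subjects, who have a device exchange prior to month 6, will be evaluated according to the original implant date". This sets the clock and does not say how the subject is scored.

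SAP 2.4.1 follows its bullets with a working rule. Its failure list has three entries: death, severe stroke, and stroke followed by death within 91 days, each before day 183 and before transplant or recovery explant. Anyone with 182 or more days of recorded follow-up and none of these is a success. Anyone who is neither is left out. Exchange is not on the list.

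Elsewhere the plan generally confines credit to the first pump. Protocol 11.2 separates Kaplan-Meier survival from success "in that post-exchange survival is considered". SAP 2.4.3 takes survival and adverse events on the original device, and SAP 3.2 stops adverse-event exposure at exchange.

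**The concern.** An exchange before Month 6 is a foreseeable failure of the originally implanted pump, and the plan gives it no single status. Under the bullets, the score of an exchanged subject turns on whether a donor heart arrives by Month 6, which is not a property of the device or the implant technique. Under the SAP working rule, exchange does not count against the subject at all, so the rule does not implement the first bullet.

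Relative to a rule that counts every exchange as a failure, both departures can only move subjects from failure to success. The trial is single-arm and compares one proportion with a fixed goal, so no comparator shares the shift. Two programmers working in good faith, one from the bullets and one from the list, could obtain different success counts from the same data.

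**Working it through.** **Step 1. How each text scores the same subject** (no severe stroke in any row).

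| Course before Month 6 | Definition bullets | SAP 2.4.1 working rule | Original device required in all routes |
|---|---|---|---|
| Exchanged, alive on second pump | Meets none | Success | Failure |
| Exchanged, then transplanted | Success | Success with 182 or more days of follow-up; otherwise neither | Failure |
| Exchanged, then explanted for recovery | Success | Success with 182 or more days of follow-up; otherwise neither | Failure |
| Exchanged, then died | Meets none | Failure | Failure |

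For example, a subject exchanged on day 60 and transplanted on day 150 satisfies the second bullet. The same subject still on the second pump at Month 6 satisfies no bullet but is a success by the working rule.

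**Step 2. Reproduce the plan's design.** Inputs from Protocol 11.2 are n = 145, goal 77.5%, expected rate 86% and a one-sided exact binomial test at 0.05. The formula is P(X ≥ r | n, p) = Σ from k = r to n of C(n,k) p^k (1−p)^(n−k).

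- The smallest r with P(X ≥ r | 145, 0.775) ≤ 0.05 is 121 (83.4%). Its exact level is 0.0494 and its exact lower limit is 77.52%.
- Power at 86% is 84.3%. Power at n = 144 is 79.2%, and from 145 on it stays at or above 80% (checked to n = 260). The stated 145 reproduces.
- One subject fewer, 120/145, gives p = 0.075.

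**Step 3. What the predecessor trial shows** (Protocol 4.2.3). At day 180, "88/140 were alive on the original device, 5/140 were alive post device exchange", and there were 8 deaths, 2 of them after exchange.

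- By subtraction, 140 − 88 − 5 − 8 = 39 subjects had been transplanted or explanted.
- 88 + 39 = 127, the reported number of successes.
- The 13 failures are 8 deaths + 5 alive after exchange, so alive on a second pump counted as failure there.
- The exchanges visible in these counts are 5 + 2 = 7, equal to the 7 malfunctions attributed to the pump. If there were no others, the number exchanged and then transplanted by day 180 was about zero. The Protocol gives no total of exchanges.

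**Step 4. Size of the shift.** Let s be the share of subjects credited despite an exchange, and suppose the rate with every exchange a failure is exactly 77.5%. The chance of passing is P(X ≥ 121 | 145, 0.775 + s).

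| Source of s | s | Subjects of 145 | Chance of passing |
|---|---|---|---|
| None | 0 | 0 | 4.9% |
| Exchanged, then transplanted or recovered (assumed) | 1% | 1.45 | 8.6% |
| Same, upper end assumed (5% exchanged × 50%) | 2.5% | 3.6 | 17.6% |
| Alive on second pump, from 5/140 | 3.6% | 5.2 | 27.1% |

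The first two non-zero rows concern the bullets. The last concerns the SAP list, which is the larger gap.

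**The case against.** The device is intended as a bridge to transplant, so reaching transplant may reasonably be called success by whatever route, and a sponsor may choose that. The exact test also keeps its 4.9% level for the endpoint as written. The percentages above compare two definitions and are not a type I error of the stated test. Both points stand. They do not explain why the SAP's list departs from its own first bullet, or which of the two governs.

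A reader might infer four stronger things that the documents do not support:

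- **That the bullets contradict the predecessor trial.** Applied to its counts they return exactly 127/140. Those counts do not show how an exchange followed by transplant would have been scored.
- **That they contradict Protocol 11.2.** That text concerns survival after exchange, which the first bullet already excludes. It does not mention transplant after exchange.
- **That Appendix D conflicts with the endpoint,** because "Urgent transplantation (immediate 1A listing for transplant") is listed beside pump replacement as a mark of major malfunction. Appendix D classifies adverse events and does not define success.
- **That the 86% and 77.5% rest on counting every exchange as a failure.** The documents do not say how such cases were scored in the data cited. If they were scored as in this plan's bullets, goal and result are on one scale.

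Parts of Protocol 11.4 and SAP 2.4.7 are redacted and may contain related analyses.

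**Conclusion.** The inconsistency is established from the text. Exchange is unaddressed in two of the three success routes, and the SAP's working rule contradicts the device condition in the remaining one. It would be too strong to say simply that a subject still on a second pump is a failure: that follows from the bullets, but the SAP rule scores the same subject a success.

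The size is uncertain. The share exchanged and then transplanted or recovered is not in the documents. I assumed 0 to 2.5%, and the predecessor counts suggest about zero, so the transplant and recovery gap is probably small. The SAP list matters more. If 3.6% of subjects are alive on a second pump, as in the predecessor trial, about five of 145 would be credited against the definition, and the chance of passing at a strict 77.5% would be 27%. With 121 passing and 120 failing, the point should be settled before the endpoint is scored.

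**What to change.** - **Definition** (Protocol 2, 6.3 and 11.1.2; SAP 1.2 and 2.4.1): state once, for all three routes, that the original pump must remain in place until Month 6, transplant or recovery explant, whichever comes first.
- **SAP 2.4.1 failure list:** add an exchange of the pump before day 183 that precedes any transplant or recovery explant. Both edits are needed. Rewording the bullets alone leaves the list scoring a subject on a second pump as a success.
- **Benchmark:** confirm that the data behind 86% and 77.5% were scored the same way. If they were not, report the exact test under the other scoring as a sensitivity analysis.

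The cost is wording and at most one extra run. SAP 3.2 already uses exchange and transplant dates. The observed success count may fall by a few subjects. If the planned 86% includes subjects credited after exchange, power at 145 under the stricter definition is lower: 79.7% if they are 0.5% of subjects, 74.4% if 1%, and 56.1% if 2.5%.
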